## 6.6 Sample Size Calculation

Assuming that the expected safety for procedures performed with the Corindus GRX system do not differ from historical performance, we set up a performance goal using the historical rate of 5% for safety and an 10% non-inferiority margin to set up a performance goal of 15% for safety. The safety hypothesis is:

$$H_0: p \geq 15\% \quad (5\% + 10\% \text{ NI margin})$$

$$H_a: p < 15\%,$$

where  $p$ =proportion of patients with a safety event.

A sample size of 96 subjects will have at least 90% power to test this safety hypothesis (PASS 14, one-sample proportion, exact test, normal approximation for power).

Assuming that the expected procedure success rate is similar to the 90% based on literature and our best estimate of possible conversion to manual procedures, we set up a performance goal using the historical rate of 90% for with a 10% non-inferiority margin to set up a goal of 80% for performance.

The performance hypothesis is:

$$H_0: p \leq 80\% \quad (90\% - 10\% \text{ NI margin})$$

$$H_a: p > 80\%,$$

*Version Date: May 21, 2021*

*This confidential document is the property of Corindus, Inc. and shall not be reproduced, distributed, disclosed or used without the express written consent of Corindus, Inc*

where  $p$ =proportion of patients with a successfully completed endovascular procedure.

A sample size of 108 subjects will have at least 80% power to test this safety hypothesis (PASS 14, one-sample proportion, exact test, normal approximation for power).

The overall trial sample size for the trial will be driven by the performance endpoint with at least 108 subjects enrolled.

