## 4. INVESTIGATIONAL PLAN

### 4.1 Overview of Trial Design

This is a prospective, single-arm, international, multi-center, non-inferiority study to gather real-world data on the effectiveness and safety of the CorPath GRX System for endovascular cerebral aneurysm embolization. Subject selection requires a clinical indication for endovascular coil and/or stent-assisted coiling embolization of cerebral aneurysms. After obtaining informed consent, performing eligibility confirmation, then screening and baseline assessments, qualifying subjects will be enrolled in the clinical investigation.

The study will be conducted at a maximum of up to 20 investigational sites. This will depend on each active site's recruitment rate and the possible travel restrictions due to the Covid-19 pandemic. Up to 120 subjects will be enrolled in order to achieve at least 108 subjects in the study; each site will try to recruit a maximum of 20 subjects. If a site has the possibility to enroll

Version Date: May 21, 2021

*This confidential document is the property of Corindus, Inc. and shall not be reproduced, distributed, disclosed or used without the express written consent of Corindus, Inc.*

more than 20 subjects, a written authorization will be required from the sponsor, Corindus, Inc. The protocol does not dictate the therapeutic decisions of the Investigators. The total expected maximum *clinical investigation duration*, including completion of all follow-up requirements, is approximately 24 months: the recruitment phase is 18 months and follow-up is 180-days. No further follow-up or additional treatment is required per the protocol, and any additional follow-up and/or treatment is at the discretion of the physician/standard hospital practices.

All enrolled subjects will be followed post-CorPath GRX endovascular procedure through 180 days post-procedure.

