3.2 Sample Size Calculation

The goal of the primary analysis will be to demonstrate that cerebral aneurysm coiling treated with CorPath GRX is as effective and safe as compared to the combined historical control treatments for cerebral aneurysm coiling treated with traditional manual operation.

For safety, if the upper bound of the 2-sided 95% confidence interval is less than the performance goal of 15%, we will conclude that the Corindus GRX system did not negatively impact safety.

For performance, if the lower bound of the 95% confidence interval for the proportion of successful patients is greater than the performance goal of 80%, we will conclude that the Corindus GRX system did not negatively impact performance.

Assuming that the expected safety for procedures performed with the Corindus GRX system do not differ from historical performance, we set up a performance goal using the historical rate of 5% for safety and an 10% non-inferiority margin to set up a performance goal of 15% for safety.

The safety hypothesis is:

$$H_0: p \geq 15\% \text{ (5\% + 10\% NI margin)}$$

$$H_a: p < 15\%,$$

where p =proportion of patients with a safety event.

A sample size of 96 subjects will have at least 90% power to test this safety hypothesis (PASS 14, one-sample proportion, exact test, normal approximation for power).

Assuming that the expected procedure success rate is similar to the 90% based on literature and our best estimate of possible conversion to manual procedures, we set up a performance goal using the historical rate of 90% for with a 10% non-inferiority margin to set up a goal of 80% for performance.

The safety hypothesis is:

$$H_0: p \leq 80\% \text{ (90\% - 10\% NI margin)}$$

$H_a: p > 80\%,$

where p =proportion of patients with a successfully completed endovascular procedure.

A sample size of 108 subjects will have at least 80% power to test this safety hypothesis (PASS 14, one-sample proportion, exact test, normal approximation for power).

The overall trial sample size for the trial will be driven by the performance endpoint with at least 108 subjects enrolled.

4 Statistical Analyses and Study Objectives

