4.2 Primary Effectiveness Endpoint

Objective: To assess effectiveness of using CorPath GRX for robotic-assisted endovascular procedure.

Hypothesis:

$H_0: p \leq 80\% \text{ (90\% - 10\% NI margin)}$

$H_a: p > 80\%,$

where p =proportion of patients with a successfully completed endovascular procedure.

Endpoint: The proportion of subjects with successful completion of the robotic-assisted endovascular procedure absent any unplanned conversion to manual for guidewire or microcatheter navigation, embolization coil(s) or intracranial stent(s) deployment, or an inability to navigate vessel anatomy.

Subjects to Include: Analysis Cohort

Statistical Analysis: The proportion of subjects with a successful procedure completion as defined will be summarized along with a 2-sided Clopper Pearson Exact 95% confidence interval. If the lower bound is greater than 80%, we will declare success and conclude that effectiveness is not inferior to the performance goal of 80%.

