4.3 Primary Safety Endpoint

Objective: To assess safety of using CorPath GRX for robotic-assisted endovascular procedure.

Hypothesis:

$H_0: p \geq 15\% (5\% + 10\% \text{ NI margin})$

$H_a: p < 15\%,$

where p =proportion of patients with a safety event.

Endpoint: The proportion of subjects with a safety event where a safety event is intra- and peri-procedural events, including target aneurysmal rupture, vessel perforation or dissection, and thromboembolic event with neurological decline within 24 hours post-procedure or hospital discharge, whichever occurs first.

Subjects to Include: Analysis Cohort

Statistical Analysis: The proportion of subjects with a safety event as defined will be summarized along with a 2-sided Clopper Pearson Exact 95% confidence interval. If the upper bound is less than 15%, we will declare success and conclude that safety is not worse than the performance goal of 15%.

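### Power was computed by normal approximation but an exact interval decides: safety power at 96 is 89.2%, not at least 90%; both targets hold at 108, but effectiveness power drops below 80% at 110 to 112

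*Protocol*

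**What the plan says.** Protocol 6.6 builds the safety goal of 15% from a "performance goal using the historical rate of 5% for safety and an 10% non-inferiority margin" and then states: "A sample size of 96 subjects will have at least 90% power to test this safety hypothesis". For effectiveness it takes an expected success rate of 90%, subtracts a 10-point margin to reach a goal of 80%, and states: "A sample size of 108 subjects will have at least 80% power". The second calculation sets the trial size. SAP 3.2 repeats both figures and gives the method as "PASS 14, one-sample proportion, exact test, normal approximation for power".

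The decision rules are exact. SAP 4.2 uses a "2-sided Clopper Pearson Exact 95% confidence interval" for effectiveness, with success if the lower limit exceeds 80%. SAP 4.3 does the same for safety: "2-sided Clopper Pearson Exact 95% confidence interval. If the upper bound is less than 15%, we will declare success". Protocol 6.1 and 6.2 also specify exact binomial intervals.

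On size, Protocol 4.1 says: "Up to 120 subjects will be enrolled in order to achieve at least 108 subjects in the study". Subjects count as enrolled when they sign consent (Protocol 4.4). The Analysis Cohort contains only those with an attempted procedure, shown by a recorded robotic microcatheter insertion time (SAP 4.1).

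**The concern.** A power statement should describe the test that will be run. Here the planning formula is smooth in the sample size, while the deciding rule moves in whole events. Exact power therefore has a sawtooth shape. While the permitted number of failures stays fixed, each extra subject lowers power; when one more failure is permitted, power jumps up.

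Two things follow. A figure that just clears its target under the approximation may not clear it under the exact rule. And a range of sizes starting at an adequate number may contain sizes that are not adequate. The second matters more here, because effectiveness drives the trial size and the plan names a minimum and a cap but no target for the number analysed.

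**Working it through.** **Inputs.** Safety: p0 = 0.15, p1 = 0.05, n = 96. Effectiveness: p0 = 0.80, p1 = 0.90, n = 108 (Protocol 6.6, SAP 3.2). One limit of a 2-sided 95% interval decides each endpoint, so one-sided alpha is 0.025 and z = 1.960. Sizes of interest: 108 to 120 (Protocol 4.1).

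**Step 1: reproduce the plan.** Normal approximation with the null variance in the critical value and no continuity correction:

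power = Φ( (|p1 − p0| − z·√(p0(1−p0)/n)) / √(p1(1−p1)/n) )

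- Safety, n = 96: (0.10 − 1.960 × 0.03644) / 0.02224 = 0.02857 / 0.02224 = 1.284, so power is 90.05%.
- Effectiveness, n = 108: (0.10 − 1.960 × 0.03849) / 0.02887 = 0.02456 / 0.02887 = 0.851, so power is 80.26%.

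Solving for n gives 95.87 and 107.43, which round up to 96 and 108. The source of the plan's figures is not in doubt.

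**Step 2: pass limits under the Clopper-Pearson rule.**

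- Safety, n = 96: 7 events give an upper limit of 14.4% (pass); 8 give 15.8% (fail).
- Safety, n = 108: 8 events give 14.1% (pass); 9 give 15.2% (fail).
- Effectiveness, n = 108: 95 successes give a lower limit of 80.3% (pass); 94 give 79.2% (fail).

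**Step 3: exact power at the stated sizes.**

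- Safety, n = 96: P(X ≤ 7 | 96, 0.05) = 89.2%. Stated: at least 90%. Shortfall 90 − 89.2 = 0.8 points.
- Safety, n = 108: P(X ≤ 8 | 108, 0.05) = 90.8%.
- Effectiveness, n = 108: P(X ≥ 95 | 108, 0.90) = 81.0%. Stated: at least 80%. Met.

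**Step 4: exact power over the permitted range.**

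| n | Effectiveness: successes needed (failures allowed) | Effectiveness power | Safety: events allowed | Safety power |
|---|---|---|---|---|
| 108 | 95 (13) | 81.0% | 8 | 90.8% |
| 109 | 96 (13) | 80.1% | 8 | 90.4% |
| 110 | 97 (13) | 79.1% | 9 | 95.1% |
| 111 | 98 (13) | 78.2% | 9 | 94.8% |
| 112 | 99 (13) | 77.2% | 9 | 94.6% |
| 113 | 99 (14) | 84.3% | 9 | 94.3% |
| 118 | 104 (14) | 80.0% | 9 | 92.8% |
| 119 | 104 (15) | 86.3% | 10 | 96.4% |
| 120 | 105 (15) | 85.6% | 10 | 96.2% |

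From 114 to 117 effectiveness power runs from 83.5% down to 80.9%. So 110, 111 and 112 are the only sizes in the range below 80%, by at most 80 − 77.2 = 2.8 points. Safety power is never below 90.4% in the range.

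**Step 5: type I error.** At the goal itself, the chance of passing is 1.78% for safety at 96, 2.10% for effectiveness at 108 and 1.37% for effectiveness at 112. The exact rule keeps it at or below 2.5% at every size.

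**The case against.** The approximation is disclosed, and by that method the figures are right. The size at which the safety statement fails is not the trial's size: the effectiveness calculation supersedes 96, and at 108 both targets are met under the exact rule. The plan attaches its 80% to 108 subjects and does not literally promise it at every size up to 120. Sawtooth power is an ordinary property of exact tests. The differences are also no larger than those from rounding the inputs. With the unrounded safety rate of 30/626, exact power at 96 is 91.0%; with the unrounded conversion rate of 99/948, exact effectiveness power at 108 is 76.4%. Finally, a sponsor cannot guarantee the number analysed, because it depends on who has an attempted robotic procedure.

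Most of this stands and sets the weight of the point. It does not remove the point: disclosing the method explains the 90% but does not make it true for the test that decides, at the 5% rate the plan itself uses. Nor does anything in the plan direct the analysed number away from 110 to 112.

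A reader might infer that both stated powers are wrong, or that the trial is underpowered as planned. The documents do not support either reading: the 108-subject effectiveness figure is slightly conservative (80.26% by the approximation, 81.0% exactly). A reader might also conclude that the sponsor should simply avoid 110 to 112. Since consent defines enrolment and an attempted procedure defines the cohort, that cannot be guaranteed.

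**Conclusion.** The point holds, at minor weight. One stated figure is not delivered by the deciding rule: safety power at 96 is 89.2% against at least 90%. Both targets are met at the planned minimum of 108. Within the permitted 108 to 120, effectiveness power ranges from 77.2% to 86.3% and is below 80% only at 110 to 112.

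This assumes true rates of exactly 5% and 90%, the Clopper-Pearson rules of SAP 4.2 and 4.3, and a final Analysis Cohort of 108 to 120. No conclusion the trial could reach is made invalid, because the exact rule controls false-positive error at whatever size is analysed.

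**What to change.** In Protocol 6.6 and SAP 3.2, replace the normal-approximation powers with exact binomial powers and give the pass limits:

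- Safety: about 89% at 96 (7 or fewer events), about 91% at 108 (8 or fewer), and at least 90% throughout 108 to 120.
- Effectiveness: 81% at 108 (95 or more successes), and 77% to 86% over 108 to 120 depending on the number analysed.

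State in advance the target number of evaluable subjects, within the existing cap of 120, and add that actual power will depend on the number in the Analysis Cohort. Of the sizes above 108, 113 (84.3%) and 119 (86.3%) sit at the top of a sawtooth step. They can serve as targets but not as guarantees. The target should be fixed before outcomes are known, since the trial is single-arm.

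The cost is a text change in two sections. Hypotheses, margins, decision rules and the cap stay as they are. The only downside is that one stated figure becomes slightly less favourable.

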## 6.7 Endpoint Analysis and Reporting

All statistical analyses will be performed using SAS Version 9.4 or higher or other valid statistical software. Descriptive summary statistics will be provided for endpoints along with 95% confidence intervals as appropriate. Subject data listings and tabular and graphical presentations (e.g., bar graphs, pie charts, line graphs) of results may also be provided.

The secondary endpoint at the nominal 90 days post-procedure (modified Rankin Score) will be reported with descriptive statistics. Secondary endpoints captured at the nominal 180-day visit will be presented in tabular format (see Table 5) where appropriate; and for Clinical assessment & Physical Exam variables, with descriptive statistics; data for Target Aneurysm Assessment will be presented in a tabular format (see Table 1).

Adverse events occurring during or before the post procedure visit identified in Table 1 will be reported separately. Adverse events occurring after this visit will be reported (1) separately and (2) pooled with prior adverse events.

An analysis of periprocedural data will be performed upon completion of the post-procedure visit of the 108th enrollment and/or enrollments that have closed. The final analysis will be performed after follow-up is completed for all enrolled subjects. A separate statistical analysis plan (SAP) will be prepared and will include additional details for planned analyses.

## 6.8 Analysis of Baseline Demographics and Procedural Characteristics

All clinically relevant baseline variables will be tabulated using descriptive statistics.

## 6.9 Handling of Missing Data

It is assumed that because the primary and most secondary analyses are evaluated within 24-hours of CorPath GRX procedure or prior to hospital discharge, whichever occurs first, there will be minimal missing data. For the 90-day and 180-day secondary endpoints (modified Rankin Scale, thromboembolic events, and aneurysm occlusion), all practical monitoring and follow-up steps will be taken to ensure complete and accurate data collection. Additionally, all data collected on safety or adverse events will be reported to the extent they are available.

# 7. DATA COLLECTION

## 7.1 Study Data Requirements

To ensure data quality and completeness, all required data will be recorded on standardized electronic case report forms (eCRFs). eCRFs must be completed for each subject and, once complete, electronically signed by the Investigator in the electronic data capture (EDC) system. The Investigator will electronically sign after all data has been entered, all queries have been resolved, and all monitoring is completed. The Investigator, or their authorized designee, is responsible for recording all study data in the eCRFs. If a paper CRF is used to capture any additional study related data, it must be signed and dated by the Investigator.

## 7.2 Data Processing & Quality Control

A full-featured relational database on a central server, networked to data entry and data analytical workstations will be employed. Conventional data verification sub-routines will be extensively programmed to test entry and logical errors, while all individual (subject based) case report forms will be linked for cross-reference. Periodic analysis of each data field (a cross cases) will be performed to examine the expected distributions of data, and to identify outliers for possible data mistakes.

## 7.3 Data Cleaning

All eCRFs will be subjected to inspection for completeness, data inconsistencies, clarity and deviations upon receipt. All deficiencies or deviations will be reported to the site as necessary. All data inconsistencies will be resolved with the revision of errant forms at the clinical site, by site

personnel.

#### **7.4 Data Entry**

Study data will be collected using electronic case report forms and a 21 CFR Part 11-compliant electronic data capture system. Part 11, Title 21 of the US FDA's Code of Federal Regulations (CFR), or FDA 21 CFR Part 11, is particularly important because it details the regulations for the use of electronic documents and signatures. The application provides the capability of data collection remotely through the Internet so the participating site personnel may log on the system securely and enter the data. All subjects' data collected in the system will be extensively verified through data validation programs, database integrity rules, and investigation-specific data entry conventions for data accuracy and logical meaningfulness. Periodic analysis of all subjects' collected data will be performed in order to examine the expected distributions of data and to identify outliers for possible data entry errors. The investigator is responsible for reviewing all eCRF entries for completion and correctness. Changes in case report forms will be made electronically and the system used will keep an audit trail of changes. If necessary, an explanation for the change(s) may be provided. All study staff who will enter data into eCRFs will undergo appropriate training for use of electronic CRFs. Further information regarding eCRF navigation and use may be found in the eCRF Completion Guidelines.

#### **7.5 Final Data Analyses**

All exported datasets for analyses will undergo a final data cleaning procedure unique to each exported dataset.

#### **7.6 Confidentiality and Protection of Study Files**

Information about study subjects will be kept strictly confidential, including their personal identity and all personal medical information. Subjects will be identified by a unique study number consisting of site number – subject ID number. The patient's consent to the use of records for data verification purposes will be obtained prior to enrollment in the trial.

The Investigator Site File will be held in a secure area. Only personnel responsible for collecting the data and transcribing it onto the case report forms will have access to the data. Records will remain on site in secure areas.

Appropriate precautions will be taken to maintain confidentiality of subject medical records and personal information. However, the subject's name may be disclosed to the Sponsor, Corindus, or health authorities if they inspect the clinical investigation records. A report of this clinical investigation may be published; however, the subjects' identities will not be disclosed.

Passwords will be issued to appropriate site, monitoring and Sponsor personnel to ensure confidentiality and protection of the data by allowing variable levels of access to the computer system. All data collection and reporting will follow strict adherence to the US Health Insurance Portability and Accountability Act (HIPAA) and EC guidelines for subject confidentiality.

## 7.7 Source Documents

Source data is all information, original records of clinical findings, observations, or other activities in a clinical trial necessary for the reconstruction and evaluation of the trial. Source data are contained in source documents. Examples of these original documents, and data records include: hospital records, clinical and office charts, laboratory notes, memoranda, subjects' diaries or evaluation checklists, pharmacy dispensing records, recorded data from automated instruments, copies or transcriptions certified after verification as being accurate and complete, X-rays, subject files, and records kept at the pharmacy, at the laboratories, and at medico-technical departments involved in the clinical trial.

The site will make available all source documents for inspection.

The following information should be included in the subject's medical record:

- Subject's name and contact information
- The fact that the subject is participating in an approved clinical investigation
- The clinical investigation title and reference number
- The date the subject was enrolled into the trial and the subject ID number
- A statement that written informed consent was obtained;
- Date of procedure and device lot number;
- Dates of all visits;
- Lists of medications;
- Documentation of Adverse Events;
- Date subject exited the clinical investigation, and a notation as to whether the subject

completed the clinical investigation or discontinued, with the reason for early termination.

### 7.8 Record Retention

In order to constitute evidence with respect to product safety or regulatory or legal compliance, the Investigator agrees to retain clinical investigation-related documents in a location that is secure and to which access can be gained if required. The following documents must be archived: Investigator's File containing all regulatory agency and required GCP documents, including, for example, signed Patient Informed Consent forms and subject-related materials, CRFs, and Data Clarification forms.

Documents should be retained by the Investigator for the appropriate period (i.e., 15 years in Europe or according to the local country regulations).

All clinical investigation-related correspondence, subject records, consent forms, records of the distribution and use of the investigational products, and copies of eCRFs should be maintained on file. Corindus requires notification in writing if the Investigator wishes to relinquish ownership of the data so that mutually agreed upon arrangements can be made for transfer of ownership to a qualified entity.

